## Key Protocol Terms

---

Term or Abbreviation	Definition
2D Imaging	Mammographic imaging on a 2D FFDM system
3D or Tomosynthesis Imaging	Mammographic imaging on a 3D or tomosynthesis system
BIRADS	Breast Imaging-Reporting and Data Systems
Breast Density BIRADS	The classification of density into 4 groups with ratings 1-4 based on the composition of the breast tissue. Where a 1 is almost entirely fatty, a 2 has scattered fibroglandular densities, a 3 is defined as heterogeneously dense, and a 4 is extremely dense
CC	Cranio- Caudal – the top to bottom view of a mammogram
Combo Images	2D and 3D images acquired under one compression
C-Paddle	Curved paddle; This is the investigational paddle.
FFDM	Full-field digital mammography
MLO	Medio-lateral Oblique- the side view of a mammogram
SOC Paddle	Standard of Care (conventional) compression paddle
Tomosynthesis	Set of images reconstructed at 1 mm intervals from a set of 2D images acquired as the x-ray source moves in an arc above the breast. The set of 1 mm images composes a 3D data set.

# Executive Overview

Protocol Version and date	Revision 3.0 Dated: January 15 th , 2018
Objective:	To evaluate a new investigational curved paddle to be used in mammography at compression forces to achieve tautness in the breast to determine a reduction in pain from the current standard of care paddle
Study Goals:	1. To achieve a mammographic procedure that reduces discomfort for patients.
Primary Endpoint:	1. Comfort with the investigational curved paddle will be improved to that of the standard paddle based on pain scale data recorded for each paddle type
Secondary Endpoint:	1. The curved paddle allows for an increase in tissue coverage as compared to the standard paddle 2. Image quality when using the curved paddle is non-inferior to the image quality of the standard paddle
Brief Inclusion/ Exclusion Criteria (see page 13- for full detailed listing)	
Inclusion Criteria
 
 
• Subject is female of any race and ethnicity
 
• Screening Subject is at least 40 years old, Diagnostic subjects are at least 25 years old
 
• Subject will be referred for a screening or a diagnostic work-up with tomosynthesis as part of the exam
 
 
Exclusion Criteria:
 
 
• Subjects who are pregnant or who think they may be pregnant
 
• Subjects lactating or presenting with discharge
 
• Women too large for the detector
 
• Subjects who cannot give informed consent
 

Number of Subjects	Up the 650 subjects at 4-5 collection sites in the United States
Study Type	Multi-Center, Controlled
Study Duration	24 months

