650 women who are at least 40 years of age will be enrolled. Data will be recorded for compression related parameters such as compression force, thickness, and comfort for both conventional and investigational paddle designs. A standardized 10 point pain scale will be used to record comfort. The investigational paddle that will be tested has been constructed with the natural shape of the breast in mind, rather than current paddles which are straight and flat to try to flatten the breast. In order to obtain the necessary information related to the images, radiologists will be asked to evaluate overall image quality between the standard of care paddle and the investigational paddle.

Each subject will be instructed on the use of the pain scale. The investigational imaging using the Curved Paddle (C-paddle) will be conducted on one breast in either the screening or the diagnostic study population for this study.

At the time of enrollment all screening subjects must be at least 40 years of age and all diagnostic patients must be at least 25 years of age, and be scheduled to have a mammogram as part of their routine clinical care. All subjects will be required to sign an informed consent form prior to enrollment and undergoing imaging with the investigational paddle in the study. All exams will be conducted on the same day. At the

conclusion of the procedure each subject will be asked a few questions related to her overall experience during the visit and her preference for which paddle she preferred.

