#### **Inclusion Criteria**

- Subject is female (born XX) of any race and ethnicity
- Screening Subjects are  $\geq 40$  years old and diagnostic subjects are  $\geq 25$  years old
- Subject will have had a combination 2D plus 3D exam
- If Subject is having a diagnostic workup she has had a 2D plus 3D imaging exam within the last 60 days
- Subject is either having a screening mammogram or presenting for a diagnostic imaging evaluation

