#### **Exclusion Criteria**

- Subject is unable or unwilling to undergo informed consent
- Subject is pregnant
- Subject is breast-feeding
- Subject is unable to be imaged on a standard detector; breasts are too large

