## **10. DETAILED STUDY PROCEDURE**

A study flow chart is shown below. The study will include 650 subjects. After determining eligibility and informed consent is obtained, the subjects presenting for screening will undergo (2D plus 3D) with the current paddle and 2 views of one breast with the curved paddle (CC and MLO in 2D plus 3D).

[figure not shown]
If the patient is undergoing diagnostic imaging she will have her prescribed diagnostic views followed by a combination (2D plus 3D) CC or MLO with both the standard paddle and the investigational curved paddle compressed to tautness on the breast of interest.

In both the screening and the diagnostic populations, the paddle order will alternate so that for the first subject the order would be standard of care, followed by the investigational paddle. The next subject would have the investigational first followed by the standard of care. The order is changed to prevent distortion in the recorded pain scores since women may find the first compression more or less painful than subsequent compressions.

Both sets of compression on the curved paddle and the standard of care paddle will be to tautness. The force will not be matched exactly since the curved compression paddle may allow imaging of more breast

tissue and forcing the compression level to match the standard of care may result in unnecessary pain to achieve tautness. The technologist will strive to achieve a similar compression without causing excess pain.

[figure not shown]
**Figure 4:** Flowchart showing the enrollment and imaging process

The technical factors such as kilovoltage, tube current and filtration will be determined using AEC (automatic exposure control) in the same manner as conventional 3D exams.

At the completion of each compression for each view and each paddle (the standard procedure and the investigational procedure(s)) each patient will be asked to rate her pain on a 0-10 pain scale. The result will be pain scores for the breast being compressed with both paddles. Additionally, each patient will be asked to point out any specific areas of discomfort on a breast diagram that is experienced during the course of the compression procedures.

**Figure 5:** Pain score used for comfort evaluation

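### The full eligibility list in Section 9.1 omits two exclusions that the Executive Overview states (possible pregnancy and discharge), and one Section 9 sentence misstates the minimum age

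*Combined protocol and SAP*

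**What the plan says.** Eligibility appears in three places in the combined protocol and SAP.

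- **Executive Overview.** The criteria are headed as brief, with the pointer "see page 13- for full detailed listing". The exclusions include "Subjects who are pregnant or who think they may be pregnant" and "Subjects lactating or presenting with discharge". Screening women must be at least 40 and diagnostic women at least 25. The woman is to be referred for an exam that includes tomosynthesis.
- **Section 9 (Study Design).** One sentence reads "650 women who are at least 40 years of age will be enrolled". A later paragraph of the same section gives 40 for screening and then says "all diagnostic patients must be at least 25 years of age". It also requires that the woman be scheduled for a routine mammogram at enrolment, and puts all exams on one day.
- **Section 9.1 (Inclusion/Exclusion Criteria).** The pregnancy exclusion is "Subject is pregnant". Breast-feeding is excluded; discharge is not mentioned. The age limits are 40 and 25. One inclusion item is "Subject will have had a combination 2D plus 3D exam"; a separate item asks diagnostic women for such an exam within the last 60 days.

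**The concern.** A summary may be shorter than the list it summarises. Here the list described as full is the one that leaves exclusions out, so a site that follows the cross-reference applies the looser rule. Section 21 has staff determine eligibility from the defined criteria, and Section 20.3.1 has the investigator check the inclusion/exclusion forms each month, so the wording of the list governs who is enrolled.

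The curved-paddle images are taken for research, and Section 14 anticipates no immediate benefit to the subject. A woman who thinks she may be pregnant is kept out by the overview, but Section 9.1 as written does not exclude her. Women of child-bearing age are expected: diagnostic subjects enter from 25, and Section 18.1 collects the day of the menstrual cycle. The public text describes no pregnancy test, so the woman's own suspicion matters as a screen.

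The discharge item is a question of population. If some sites exclude these women and others do not, the pain result describes a different mix of women from site to site.

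**Working it through.** No sample-size, power or alpha figure is involved. The check sets the passages side by side.

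| Item | Executive Overview | Section 9 | Section 9.1 |
|---|---|---|---|
| Pregnancy | pregnant or possibly pregnant excluded | not addressed | pregnant excluded |
| Lactation, discharge | lactating or discharge excluded | not addressed | breast-feeding excluded |
| Minimum age | 40 screening, 25 diagnostic | one sentence: 40 for all 650; later sentence: 40 and 25 | 40 and 25 |
| Exam | referred for it | scheduled | "Subject will have had a combination 2D plus 3D exam" |

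**Pregnancy.** Take a woman who suspects pregnancy but has no confirmation. The overview excludes her; Section 9.1 does not.

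**Discharge.** Take a woman with discharge who is not breast-feeding. The overview excludes her; Section 9.1 does not.

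**Age.** Three statements (the overview, the later Section 9 sentence and Section 9.1) agree on 40 and 25; one stands against them. The odd sentence is the stricter, so following it would turn away diagnostic women aged 25 to 39. It cannot admit anyone whom the overview excludes.

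**Exam.** For a screening woman the Section 9.1 item has three possible readings.

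1. The exam is done by the end of the visit. This raises no difficulty.
2. She had such an exam on some earlier occasion. This leaves paddle order free but adds a requirement that the overview does not contain.
3. The standard exam of this visit is complete before she qualifies. This would rule out curved-first order.

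The third reading does not fit the rest of the plan. Section 10 alternates order in both populations, and of the second subject it says: "The next subject would have the investigational first followed by the standard of care". Section 9 treats the exam as scheduled at enrolment and puts all imaging on the same day. For diagnostic women the 60-day exam is separate from the two-paddle comparison, so curved-first order is open to them on any reading.

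All four differences are in the current text; none comes from the revision summary.

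**The case against.** The overview is part of the protocol, so a careful site could apply both lists together and exclude everyone whom either one excludes. The site's inclusion/exclusion form is not in the public documents and the consent pages have been removed, so either may already carry the fuller pregnancy wording. This stands as a limit on what can be said about practice. It does not remove the contradiction, because the overview itself names the other list as the full one.

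Each woman is her own control, so differences in who enters do not bias the paddle comparison within a woman. That also stands: the discharge and age items bear on whom the result applies to, not on its internal validity.

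The documents do not give radiation as the reason for the overview's exclusions. The link is a reasonable inference for possible pregnancy and has no textual basis for discharge.

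Two stronger readings are tempting, and the documents support neither.

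- A reader might infer that Section 9.1 forces standard-first order in screening women and so biases the pain comparison. Sections 9 and 10 show otherwise. Any figure for such a bias would also need an order effect and a screening share, and the documents state neither.
- A reader might attach the added breast dose in Section 14.1 (2 x 2.9 = 5.8 mGy) to every wrongly admitted woman. That figure is for two investigational views, which is the screening schedule. Diagnostic women have one view with the curved paddle, and Section 14.1 gives no separate figure for them. A breast dose does not measure a pregnancy risk in any case.

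**Conclusion.** The eligibility criteria are internally inconsistent and should be reconciled. Two exclusions in the overview are missing from the list it calls full. The possible-pregnancy item carries the weight, because under Section 9.1 a site can give research-only imaging to a woman whom the overview keeps out. The discharge item changes the enrolled population only. The age sentence is a minor correction, and the exam wording needs clarification and no more.

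The number of women affected cannot be estimated: the documents give no screening-to-diagnostic split and no frequency for possible pregnancy or discharge. The conclusion assumes that sites treat Section 9.1 as the operative list, as the overview's cross-reference directs, and that no document outside the public text already supplies the missing items. Which version of each exclusion is right is not judged here.

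**What to change.** - Reconcile the passages into one list and use it word for word in the Executive Overview, Section 9.1 and the site eligibility form.
- Have the sponsor and IRB settle the possible-pregnancy and discharge items, so that each either appears in every place or in none.
- Replace the Section 9 sentence that sets 40 for everyone with the two age limits already stated in Section 9.1.
- As a clarification only, align the Section 9.1 exam item with Section 9, where the mammogram is scheduled at enrolment, so that it cannot be read as barring curved-first order in screening women. The separate 60-day item for diagnostic women already stands and needs no change for this purpose.

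The cost is protocol wording and one revised form. Depending on what the sponsor and IRB decide, a few women may become ineligible. No analysis changes.

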## **1. INTRODUCTION**

Routine two-dimensional x-ray mammography has been used for the screening and diagnosis of breast cancer for approximately 30 years, and is accepted as the best test for the early detection of breast cancer for the general population. The effectiveness of screening, however, is greatly dependent on sustained compliance to yearly screening, which is reportedly approximately 64% in the United States [1]. The evolution of mammography technology has seen improvements over time, culminating in the introduction of full-field digital mammography systems in 2000 and the approval of 3D imaging, or Breast Tomosynthesis in 2011. Despite vast improvements in image quality and the change to digital acquisition, an element of breast imaging that has seen very little investigation or progress is the optimization of breast compression. The woman's perception of breast compression during mammography ranges from mild discomfort to severe pain [2] and breast compression has been shown to be a barrier to compliance for routine screening [3]. The MammoPad, a soft cushion that attaches to the detector has had some degree of success to address discomfort from the detector and edges, but there has been limited changes to the design of the compression paddle to offer a decrease in discomfort for patients.

Furthermore, whereas analog film mammography required flat paddles for good image quality, digital mammography and in particular tomosynthesis imaging do not have this requirement. This leaves open the opportunity to investigate curved paddles that may improve patient comfort without adversely affecting image quality.

## **2. OBJECTIVE**

The goal of this study is to evaluate patient comfort during compression with a standard flat mammographic paddle and an investigational curved paddle. This is a study that will be performed with x-ray imaging and will be used to determine if an overall reduction in pain can be appreciated in patients without loss in image quality as compared to the current standard mammogram. Another benefit of the curved paddle may be an increase of perceivable and measurable tissue capture.

## **3. BACKGROUND INFORMATION**

Imaging the breast is complex. The breast varies widely in size, composition and glandular to fat ratio over the female population and breast cancer varies in presentation. The breast differs in consistency from quite firm and fixed on the chest wall to soft and malleable, able to be pulled easily from the chest wall.

[figure not shown]
Breast compression reduces motion un-sharpness by immobilizing the breast, decreases breast thickness reducing exposure time, geometric un-sharpness, dose and unwanted scatter radiation, and creates a more homogeneous thickness for uniform x-ray exposure, thereby allowing a relative assessment of breast tissue. Another important contribution resulting from breast compression is the separation of glandular structures, which reduces structure overlap (structure noise). Structure noise has been shown to reduce the accuracy of mammography as overlapped structures can imitate as well as hide a cancer or

an area of suspicion. Compression also aids in pulling and holding the breast forward onto the image receptor.

Two-dimensional full-field digital mammography resolves some of the issues of its analog counterpart. Because of the limited dynamic range of analog film imaging it was necessary to compress the breast to nearly uniform thickness. The wider dynamic range of digital mammography and the ability to post-process the image reduces the need for uniform compression thickness. However, digital mammography is a two-dimensional technology and is still confounded by structure noise.

Three-dimensional (3-D) breast imaging referred to as breast Tomosynthesis [4-11] has been approved by the FDA for breast cancer screening in combination with digital mammography. With tomosynthesis, the breast is imaged from a number of different angles and from these images a series of 1-mm reconstructed slices are created and combined with the ability to scroll through each slice. 3-D reduces the problem of structure noise that may hide a breast cancer or cause unnecessary recalls. Some compression of the breast tissue will be needed with both 2D and 3D imaging to hold the breast stationary and to reduce overall thickness.

**Figure 1:** Acquisition of breast tomosynthesis image. Projection images are acquired as the x-ray tube moves in an arc above the breast. These projection images are reconstructed to create the reconstructed slices.

**Figure 2:** Hologic Dimensions tomosynthesis system. This system will obtain both 2D and 3D images.

### 3.1 Current Compression Standards and Methods

For standard mammography, the breast is positioned on the image receptor, with compression applied from above using a flat, clear, minimally attenuating plastic paddle, which normally remains parallel to the image receptor. The technologist typically holds the breast in place on the image receptor and applies compression using a foot control that controls the compression force until the compression paddle is holding the breast in position. Once the breast is held in place, the technologist then may apply final compression electronically, or manually with hand-controls. As force is applied, the breast thickness is reduced and the breast spreads out allowing better visibility of internal breast structures. MQSA (Mammography Quality Standards Act) mandates technologist training for breast positioning and compression. MQSA [13] loosely provides guidelines for the compression of the breast, stating only, "A compression force of at least 111 newtons (25 pounds) shall be provided" and

“the maximum compression force for the *initial* power drive shall be between 111 newtons (25 pounds) and 200 newtons (45 pounds).” There is no recommendation for applied final force and no correlate between force, compression thickness, dose, breast spread and tissue separation.

#### **4. STUDY RATIONALE**

Despite improvements in image acquisition and display methods, compression is still applied to 3D and 2D digital imaging as it was for 2D analog imaging and has changed little over the last 30 years. One company (Hologic, Inc., Bedford, MA) has taken advantage of the post-processing of digital imaging employing a “flex” paddle, which is similar in appearance to the standard compression device, but flexes as the breast is compressed. This provides better compression at the anterior breast in women with firm breasts and a slight improvement in comfort for the patient. Another company developed and implemented single-use, minimally attenuating cushions (BioLucent, CA) that may be applied above and/or beneath the breast. However, the cushion applied above the breast is rarely used, as it impedes positioning. Small gains in patient comfort are realized with the use of the lower pad.

The amount of required compression applied is subjective and continues to be a barrier to screening due to the perception women have or from having experienced pain during screening procedures. Most technologists that perform imaging aim to achieve tautness of the breast to demonstrate adequate compression force.

Standard compression methods apply most of the compression to the central portion of the breast since the breast is thicker in the center. The curved compression paddles being investigated allow for a more even compression of the breast.

The primary aim of this research is to determine if the curved paddle will provide an improvement in patient comfort without a loss in image quality.

## 5. PRIMARY HYPOTHESIS

The patient reported pain score will decrease with the use of the investigational curved paddle compared to the patient reported pain score reported with the use of the current standard of care paddle.

## 6. INVESTIGATIONAL DEVICE DESCRIPTION

Image processing software and an investigational curved paddle will be employed on a commercially approved Hologic Selenia Dimensions mammography system. The investigational paddle is made from a plastic material shaped with a curve to conform better to breast anatomy. The breast tomosynthesis system is a digital mammography system that is capable of producing standard two-dimensional (2D) images and three-dimensional (3D) tomosynthesis images. The Hologic Dimensions system is a commercial product approved by the FDA. The image processing software will only be applied to images acquired with the investigational paddle which is identified via an RFID tag on the paddle when it is attached to the Dimensions.

**Figure 3:** Investigational paddles of different sizes showing the curved shape

## **7. DATA ANALYSIS**

### **7.1 Primary Endpoint**

The curved paddle results in less discomfort than the standard paddle in screening and diagnostic patients as demonstrated by comparing pain scores between the 2 paddles on each patient. Statistical analysis with a students paired t-test and ANOVA analysis to compare the pain scores from the current flat paddle to the new curved paddle will be conducted.

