## **9. STUDY DESIGN**

The study will be conducted in the United States at up to 5 centers. The study will enroll up to 650 subjects. The number of subjects was chosen to allow evaluation of screening and diagnostic patients with a variety of breast densities (fatty, scattered densities, heterogeneously dense or extremely dense) and women with a range of breasts sizes that fit on the current detector. The evaluation of pain reduction will be the primary endpoint, while examining the potential of increased tissue capture without a compromise in image quality will be assessed as secondary endpoints. The enrollment will be consecutive for subjects who sign informed consent to participate. Women participating in the study will present for a screening or diagnostic imaging exam.

All women participating in this study will undergo imaging with the standard and the investigational paddles in a randomized order. This is so that neither the standard paddle nor the investigational curved paddle always have a set order. The intent to randomize is to reduce any bias for either paddle; in that if one is always first the second compression may be more painful, because the woman has been under compression for a number of minutes before having the second set of compressions taken.

Each patient who agrees to participate and is consented and is undergoing a routine screening mammogram will receive 4 view 2D plus 3D combination imaging (LCC, LMO, RCC, RMLO) mammogram, with the current standard paddle. In addition she will also receive a cranio-caudal (CC) and a mediolateral oblique (MLO) in one of her breasts as determined by a randomization scheme with the investigational curved paddle. The amount of compression applied to both mammograms will be that to achieve tautness.

Patients who agree to participate, are consented and are undergoing a diagnostic exam will have diagnostic 2D plus 3D combination imaging as well as a CC or MLO with both the standard paddle and the investigational curved paddle compressed to tautness on the breast of interest. The order of the paddles will be randomized and the view (CC or MLO) will be based in the visibility of the area of interest for which the diagnostic imaging was ordered. (It is possible that one of the views is superior to assess the area of interest).

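### The paired t-test for pain ignores paddle order, which the design deliberately varies; the ANOVA's factors and the deciding analysis are not stated

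*Combined protocol and SAP*

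**What the plan says.** Section 7.1 bases the primary endpoint on "comparing pain scores between the 2 paddles on each patient" and names the method as "Statistical analysis with a students paired t-test and ANOVA analysis to compare the pain scores". It gives no model terms, does not rank the two analyses, and states neither an alpha level nor sidedness. Section 5 states a directional hypothesis: pain falls with the curved paddle. Section 11 adds descriptive summaries with 95% confidence intervals and says that no power calculation was done because the trial is descriptive.

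The design sections expect order to matter. Section 9 explains the varied order: "in that if one is always first the second compression may be more painful". Section 10 says: "The order is changed to prevent distortion in the recorded pain scores since women may find the first compression more or less painful".

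They describe the assignment differently. In section 9 women "will undergo imaging with the standard and the investigational paddles in a randomized order". In section 10 "the paddle order will alternate so that for the first subject the order would be standard of care".

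The two populations also meet the study paddles in different settings. A screening woman "will receive 4 view 2D plus 3D combination imaging (LCC, LMO, RCC, RMLO) mammogram, with the current standard paddle", plus two curved-paddle views of one breast. For a diagnostic woman, "she will have her prescribed diagnostic views followed by a combination (2D plus 3D) CC or MLO with both the standard paddle" and the curved paddle. Section 10 has pain scored on a 0-10 scale after every compression, by view and by paddle.

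**The concern.** The trial is a two-period within-woman comparison whose own rationale is a possible period effect. Varying the order stops that effect from favouring one paddle, but it does not remove the effect from the spread of the differences. Women with the curved paddle second have their difference shifted one way, and women with it first are shifted the other way. A paired t-test counts that known, assigned separation as random error.

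Three gaps add to this.

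- **Deciding analysis.** Two analyses are named, one with unstated factors, and neither is designated as deciding the directional claim. The choice stays open until the data are seen.
- **The difference itself.** The wording of section 7.1 implies one difference per woman. A screening woman yields a CC and an MLO difference and a diagnostic woman yields one, but no rule forms the single value.
- **Order effect by population.** Diagnostic women have already been compressed for their prescribed views before either study paddle. Screening order is set around a four-view standard exam. An order effect could therefore differ between the two groups.

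At stake are precision, power and the actual coverage of the promised confidence interval. How the t-test behaves depends on whether order alternates or is randomised, which the protocol leaves in conflict.

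**Working it through.** **Inputs.** N = 650 comes from section 11. The documents give no SD, order effect, correlation between views, population mix or target difference, so there is no planned figure to reproduce. Everything below except N is an assumption: within-order SD of the difference s = 2 (range 1.5 to 2.5), order effect p = 0.5 or 1 point (second set minus first, either sign), two-sided 5% level.

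**Model.** Let D = curved minus standard pain for one woman, and t the true paddle effect. D has mean t + p if standard came first and t − p if curved came first. With equal numbers in each order:

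- the mean of D is t, so both analyses are unbiased;
- the paired t-test uses variance s² + p², and the order-adjusted analysis uses s²;
- the inflation is f = 1 + p²/s².

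| | s = 2, p = 0.5 | s = 2, p = 1 |
|---|---|---|
| f | 1 + 0.25/4 = 1.0625 | 1 + 1/4 = 1.25 |
| CI width ratio, √f | 1.031 | 1.118 |
| Women needed with adjustment for the same width, 650/f | 612 | 520 |
| Type I error, alternation: 2[1 − Φ(1.96√f)] | 4.3% | 2.8% |
| Coverage of nominal 95% CI, alternation | 95.7% | 97.2% |
| Power where adjusted has 80%, alternation: Φ(2.80 − 1.96√f) | 78.3% | 72.9% |
| Same, simple randomisation: Φ(2.80/√f − 1.96) | 77.6% | 70.7% |

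For s = 1.5, f is 1.11 and 1.44, and power under alternation is 76.9% and 67.2%. For s = 2.5, f is 1.04 and 1.16, and power is 78.9% and 75.5%.

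**Why the assignment method matters.** Under alternation the order split is fixed, so the true sampling variance of the mean difference is s²/N. The t-test estimates (s² + p²)/N and is conservative. Under simple randomisation the split varies from trial to trial, the larger variance is real, and the test holds 5% but loses power.

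**Detectable difference at 80% power (N = 650, s = 2, alternation).**

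- Adjusted: 2.80 × 2/√650 = 0.220 point.
- Paired t: (1.96√f + 0.84) × 2/√650 = 0.225 point (p = 0.5) or 0.238 point (p = 1).

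**Balance.** If 5 sites each ran one alternating list per population (an assumption), at most 10 of 650 women would be unpaired in order. The bias would be at most 10/650 = 0.015 point at p = 1. In general the bias is p(2q − 1), where q is the share with curved second. A 55:45 split among analysed women with p = 1 would give 1 × (1.10 − 1) = 0.10 point, and a simulated type I error of about 19% for the paired t-test against about 5% with adjustment. Nothing in the documents predicts such drift.

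**Order effect differing by population.** This was simulated with 20,000 runs, N = 650, alternation, single-view SD 2, CC-MLO correlation 0.5 and HC3 standard errors. The SD of a screening woman's two-view mean difference is then 2 × √0.75 = 1.73, so these figures are not on the same SD as the table above. Each cell gives paired t / order + population / plus order-by-population.

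| Order effect (screening, diagnostic); share diagnostic | Type I error, % | Power at a true difference of 0.2, % |
|---|---|---|
| 1, 1; 20% | 2.4 / 4.7 / 4.7 | 72.6 / 80.9 / 80.9 |
| 1, 0; 20% | 2.7 / 4.2 / 4.8 | 74.6 / 79.8 / 81.2 |
| 0, 0; 20% | 5.0 / 4.9 / 4.9 | 81.0 / 80.9 / 80.8 |
| 1, 0; 50% | 3.6 / 4.2 / 4.9 | 72.6 / 75.0 / 77.1 |

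With no order effect, adjustment costs essentially nothing.

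**The case against.** The strongest reply is that little is lost. The design already guards against order bias, and under alternation the t-test errs against the sponsor's own claim. The loss also matters only for small differences. With s = 2 and p = 1 under alternation, a true difference of 0.3 gives 96.9% power adjusted and 94.9% unadjusted, and 0.4 gives 99.9% and 99.8%. All sizes rest on assumed values, the trial calls itself descriptive, and the ANOVA may have been meant to carry order. The order-by-population term adds only 1.4 power points (79.8% to 81.2%) in a hypothetical scenario.

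Most of this stands as a limit on size. The gain is modest, and it is negligible if the true difference is 0.4 point or more. It does not remove the point. Sections 5 and 7.1 make a directional claim backed by named tests, and section 11 promises 95% intervals, which would be too wide under alternation if order matters. An ANOVA with unstated factors cannot be credited with an order term. The interaction costs one degree of freedom and brings type I error closest to 5% when the order effects differ.

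A fair point in the other direction is that the absence of bias depends on order staying near-balanced among the women analysed. Adjustment also protects against drift from that.

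**Conclusion.** The concern holds. The paired t-test leaves out a factor that the protocol assigns because it may affect pain, and the plan does not say what the ANOVA contains or which analysis decides. With near-balanced order the consequence is lost precision, with no bias and no excess of false positives. At an assumed SD of 2, the variance is 6% or 25% larger for an order effect of 0.5 or 1 point, and the interval 3% or 12% wider. Over SDs of 2.5 down to 1.5 the inflation runs from 4% to 11% for 0.5 point and from 16% to 44% for 1 point. If there is no order effect, nothing is lost. This should be fixed because the remedy is almost free, and the same edit settles which analysis decides and how the difference is formed.

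**What to change.** Name one deciding analysis in section 7.1, for example:

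> For each woman, D is curved minus standard pain on the study breast for the same view: the mean of the CC and MLO differences for screening women (or the one available matched view), and the single-view difference for diagnostic women. D is regressed on paddle order (+1 standard first, −1 curved first), population (indicator centred at its sample mean) and their product, with heteroskedasticity-robust standard errors. The intercept is the paddle effect. The endpoint is met if its two-sided 95% confidence interval lies wholly below 0. The ANOVA is supportive, with its factors stated.

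Robust standard errors are needed because D averages two views in one population and uses one in the other. Centring makes the intercept the effect at the enrolled mix of populations.

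Also:

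- reconcile the randomised order in section 9 with the alternation in section 10;
- confirm that paddle order is captured for each woman, since the data lists in sections 9 and 18.1 do not name it, though they are not exhaustive.

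The cost is a few lines of analysis text and three degrees of freedom out of 650, with no extra patients or imaging.
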